While every OBI undergoes a thorough quality control process before being distributed into the market, issues such as leakage, the device coming loose from the skin, or other device issues, may occur. These device issues can result in medication errors which are defined as an 'unintended failure in the drug treatment process that leads to, or has the potential to lead to, harm to the patient' (EMA, 2015). Examples for medication errors that may occur as the result of an issue with the device are missed or partial doses of pegfilgrastim which put patients at increased risk of a serious infection if a replacement dose isn't administered.

"Medication errors including underdose-On-body Injector, resulting in lack of efficacy" is an important identified risk in the Neulasta EU Risk Management Plan. In the clinical trial setting, no adverse events within the MedDRA Medication errors Standardised MedDRA Query (SMQ) were reported in 262 subjects who received at least 1 dose of pegfilgrastim via the OBI and among 339 subjects administered placebo via the OBI, 1 subject (<1%) experienced a medication error. A recent study that specifically evaluated the performance of the OBI device in healthy subjects reported that 292 of 297 administrations (98.3%) were successful, while five were considered unsuccessful: two due to hazard alarms, and three due to substantial leakage (Joshi et al. 2017).

Cases of medication errors including underdose events have been reported in the US post-marketing setting after approval of OBI in December 2014. Cumulatively through 31 January 2018, the most frequently reported medication error events in the post marketing setting were events with the preferred terms "wrong technique in product usage process", "drug dose omission", and "underdose".

Risk minimisation activities to address medication errors involve routine measures (eg. product label, Instructions for Use and the Patient Leaflet), as well as an aRMM in the form of a PAC that further supports patients in the safe and appropriate use of the Neulasta OBI. The PAC is printed in color on a wallet sized tri-fold card, and is intended for patients to keep with them as a reference.

Page 16 of 61

Protocol Number: 20170701 Date: 10 April 2019

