9.3 Variables

Variables collected in the respondent questionnaire, to be administered approximately 27 to 72 hours after OBI application, will include:

- Respondent demographics and characteristics, including age, sex, educational level, self-reported language skills, self-reported confidence to monitor the OBI, health literacy - using the questions from the Brief Health Literacy Screen (BHLS) questionnaire (Chew et al. 2004) -, respondent type (patient or caregiver)
- Respondent prior use and/or monitorisation of the Neulasta OBI
- Details of respondent receipt and use of the PAC
- Respondent reported awareness of key safety messages in the PAC (eg, OBI alerts for Neulasta dose delivery or issues, time of removal of OBI, etc.)
- Respondent reported behavioural intent to carry out recommended actions as described in the PAC (eg, symptoms related to infection, issues with Neulasta dose delivery via the OBI, etc.)
- Device issues experienced by the patient (eg, whether the device came loose, red light came on, leakage, etc.) and any resulting actions*
- Symptoms of adverse events potentially related to medication errors experienced by the patient (eg, fever, chills, sweating, etc.) and related consultations with HCPs*
- Details on dose delivery (eg, expected dose delivered on time, partial dose received, etc.)*
- Occurrence of a replacement G-CSF dose (eg, type of replacement and timing)*

In addition, the HCP will report the following variables through an eCRF, to be completed at the time of respondent identification and consent:

- HCP and site characteristics (only reported once per HCP)
- HCP awareness of methods to obtain the PAC
- Date and time of OBI application
- Device issues observed by the HCP at the time of OBI application (eg, the device coming loose, problems filling the device, leakage, etc.)

^{*} Indicates variables to be collected in the partial respondent questionnaire

Date: 10 April 2019 Page 22 of 61

9.3.1 **Exposure Assessment**

Product: Pegfilgrastim

Patients included in the study will have been administered the OBI as per routine clinical practice.

9.3.2 **Outcome Assessment**

The primary endpoint for the respondent questionnaire is:

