11.1.3 Other Safety Findings

Other Safety Findings (regardless of association with an adverse) include:

 Medication errors, overdose, whether accidental or intentional, misuse, or abuse, involving an Amgen product,

- Pregnancy and lactation exposure,
- Transmission of infectious agents,
- Reports of uses outside the terms for authorized use of the product including offlabel use,
- Occupational exposure,
- Any lack or loss of intended effect of the product(s).

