11.2 Safety Collection, Recording and Submission to Amgen Requirements

This study is collecting information from patients (or their corresponding caregivers) and from HCPs at the time of Neulasta OBI application and at a point in time following Neulasta OBI administration. All safety events (adverse events, product complaints and other safety findings) considered to have occurred following subject exposure to the Neulasta OBI will be collected from Neulasta OBI application and within the following 72h with the exception of the protocol exempted events **listed below**. **IQVIA** is responsible for recording safety events that they become aware of during study period in the patient's appropriate study documentation. **IQVIA** will be responsible for reporting to Amgen any available preliminary information on a suspected safety event **that is considered serious**, within 1 business day of vendor awareness. **Non-serious Adverse events (AEs) must be reported in an expeditious manner, not to exceed 15 calendar days of** vendor awareness.

Date: 10 April 2019 Page 40 of 61

Protocol Exempted Events

Adverse events that are anticipated to occur in this study population because they are known adverse reactions to chemotherapy or are known to occur in the context of the underlying disease are not planned to be collected in this study. A list of all events and corresponding MedDRA preferred terms that are not to be collected in the study is provided in Appendix G.

If any of the exempted events have a fatal outcome, they should be considered a serious adverse event and must be collected and reported individually within 1 business day of vendor awareness unless the event is due to disease progression.

All safety information that is not specified in this section including all fatal events are to be collected and submitted to Amgen within the specified time frame.

Protocol exempted events and safety events that are suspected to be related to any medicinal product other than Neulasta OBI should be reported to the local authority in line with the local country requirements.

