Alkaline phosphatase	Blood alkaline phosphatase abnormal, blood alkaline phosphatase increased, blood alkaline phosphatase decreased
Bilirubin	Blood bilirubin abnormal, blood bilirubin decreased, blood bilirubin increased, blood bilirubin unconjugated abnormal, blood bilirubin unconjugated increased, blood bilirubin unconjugated decreased, blood bilirubin conjugated abnormal, blood bilirubin conjugated increased, blood bilirubin conjugated
Albumin	Blood albumin abnormal, blood albumin decreased, blood albumin decreased, hyperalbuminaemia, hypoalbuminaemia
Total protein	Hyperproteinaemia, hypoproteinaemia,

10 April 2019 Page 61 of 61

Event	MedDRA PT(s)
Magnesium	Blood magnesium abnormal, blood magnesium decreased, blood magnesium increased, protein total abnormal, protein total decreased, protein total increased
Phosphorus	Blood phosphorus abnormal, blood phosphorus decreased, blood phosphorus increased, hyperphosphataemia, hypophosphataemia
LDH	Blood lactate dehydrogenase abnormal, blood lactate dehydrogenase increased, blood lactate dehydrogenase decreased
Uric acid	Blood uric acid abnormal, blood uric acid decreased, blood uric acid increased, hyperuricaemia
CEA	Carcinoembryonic antigen abnormal, carcinoembryonic antigen increased, carcinoembryonic antigen high, carcinoembryonic antigen decreased
CA 19-9	Carbohydrate antigen 19-9 increased
CA 27-29	Carbohydrate antigen 27.29 increased
CA 15-3	Carbohydrate antigen 15-3 increased
Blood culture	Blood culture negative, blood culture positive
Urine culture	Urine culture negative, urine culture positive
Sputum culture	Sputum culture positive
Stool culture	Stool culture negative, stool culture positive
Seizures	Seizure
Epilepsy	Epilepsy
Hearing loss	Hypoacusis, deafness
Loss of vision	Visual impairment, blindness
Diplopia	Diplopia
Conjunctivitis	Conjunctivitis, adenoviral conjunctivitis, conjunctivitis bacterial, conjunctivitis viral
Excessive tearing	Lacrimation increased
Hand foot syndrome (Palmar- plantar dysesthesia)	Palmar-plantar erythrodysaesthesia syndrome
Lower/upper extremity swelling	Limbal swelling, oedema
Acid reflux	Gastrooesophageal reflux disease

Date: 10 April 2019 Page 1 of 9

Amendment 1

Protocol Title: An Observational Study to Assess the Effectiveness of the Neulasta[®] Patient Alert Card and to Measure Medication Errors Related to the Use of the Neulasta[®] On-Body Injector

Amgen Protocol Number Pegfilgrastim 20170701

Amendment Date: 10 April 2019

Rationale:

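### Appendix G exempts positive cultures and some localising signs of infection, and Section 11.2 lifts the exemption only for a death not due to disease progression, even after a reported delivery failure

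*Protocol*

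**What the plan says.** Section 11.2 (Protocol Exempted Events) sets aside events expected from chemotherapy or from the underlying disease. These "are not planned to be collected in this study", and Appendix G lists them by preferred term. One condition brings an exempted event back: a fatal outcome, unless the death is due to disease progression. The section gives no override for a serious non-fatal event, and none for an event after a device issue or an incomplete dose. Exempted events are to be reported to the local authority as local rules require.

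The infection-related rows in Appendix G are:

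- "Blood culture negative, blood culture positive"
- "Urine culture negative, urine culture positive"
- "Sputum culture positive"
- "Stool culture negative, stool culture positive"
- conjunctivitis, including its bacterial and viral terms
- productive cough, increased sputum and dysuria

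Elsewhere, Section 7.1 gives as examples of medication errors "missed or partial doses of pegfilgrastim which put patients at increased risk of a serious infection" when no replacement is given. It also records underdose with resulting lack of efficacy as an important identified risk. Section 9.3 collects "Symptoms of adverse events potentially related to medication errors experienced by the patient", with fever, chills and sweating as examples, in both the full and the partial questionnaire. Section 11.1.3 lists lack or loss of the intended effect among the other safety findings. Section 9.7.3 says that all adverse events reported in the questionnaire will be coded and tabulated.

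**The concern.** The reason given for the list is that these events are expected from chemotherapy or the cancer. That reason is weaker after a failed or partial G-CSF delivery, because the same event may then reflect the missing protection that Section 7.1 describes. The protocol does not say which rule governs in that case. Under Section 11.2 and Appendix G a positive blood culture in a hospitalised patient whose injector leaked is exempt. Under Section 11.1.3 the same episode could be a lack of effect and so be collected. Under Section 9.7.3, if the respondent reports it, it is coded with everything else. Two sites could handle the same event differently, and both could cite the protocol.

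The adverse-event table is the part of the report that can describe what happened to patients after the errors the study counts. If some infection evidence is removed by rule, the table understates those consequences and the reader has no sign of it.

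**Working it through.** The protocol gives no figure to reproduce for this point. The check is a comparison of texts, followed by a rough statement of scale.

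**1. What is exempted.** Positive cultures of blood, urine, sputum and stool are on the list. So are bacterial and viral conjunctivitis, productive cough, increased sputum and dysuria.

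**2. What is not exempted.** The patient alert card (Appendix F) gives fever, chills and sweating as its examples of infection symptoms. None of the three is in Appendix G. Section 9.3 collects them, with related consultations, at every application. Sepsis, pneumonia and febrile neutropenia are not on the list. Lack of effect and medication error are not on it either.

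**3. What the override covers.**

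| Event after a reported delivery failure | Collected under Section 11.2? |
|---|---|
| Fever, chills, sweating | Yes, not listed |
| Sepsis, pneumonia | Yes, not listed |
| Positive blood culture, fatal, not disease progression | Yes, override |
| Positive blood culture, serious, non-fatal | No |
| Productive cough or dysuria without a diagnosis | No |

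The gap is the last two rows.

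**4. Which results depend on the gap.** The objectives in Sections 8.1 to 8.3 are awareness and intent, receipt of the card, the proportion of administrations with medication error, and device issues at application. None is computed from an exempted term. The adverse-event summary in Section 9.7.3 is affected.

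**5. Scale.** Inputs: 80 respondents and 3.5 applications each (Section 9.5); 5 unsuccessful administrations of 297 in healthy subjects (Section 7.1).

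- Maximum applications: 80 × 3.5 = 280.
- Benchmark failure proportion: 5/297 = 1.7%.
- Expected failures at the maximum: 280 × 5/297 = 4.7.
- Expected failures with one application per respondent: 80 × 5/297 = 1.3.

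These figures assume that the healthy-subject benchmark carries over to patients in routine care. They show only that delivery failures will be few. The protocol gives no probability of infection, or of a positive culture, after a failure, so the number of lost events cannot be derived.

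**6. Observation time.** Safety events are collected for 72 hours from application, and delivery is expected at 27 hours. That leaves 72 − 27 = 45 hours after expected delivery. Section 9.9.1.1 already acknowledges that this is short for an infection to develop.

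**The case against.** The strongest reply is that the list is a deliberate choice of scope with a stated reason, and that little is lost. The symptoms the card itself names, and the consultations they lead to, are recorded at every application. Most infection diagnoses remain reportable. No data source planned in Section 9.3 asks for culture results, so these could reach the study only spontaneously or through follow-up information. Whether the questionnaire elicits cough or dysuria is not known from the protocol, because it is a stand-alone document.

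Most of this stands, and it limits the size of the point. It does not remove it. Section 11.2 allows the HCP to be asked for a discharge summary or record extracts, so culture results can arrive, and the rule then excludes them. The short window is disclosed as a limitation, whereas the removal of infection evidence through Appendix G is not.

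A reader might also call the passages a flat contradiction. That goes further than the text. Section 7.1 states a risk rather than a collection rule, the examples named in Section 9.3 are still collected, and a suspected loss of effect can be reported under its own heading. The accurate statement is that Section 11.2 and Appendix G sit badly with Sections 7.1, 11.1.3 and 9.7.3, and that nothing says which prevails.

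**Conclusion.** The point holds in a limited form. As written, a serious non-fatal culture finding, or a localising symptom without a diagnosis, is outside collection even when a delivery failure has been reported for that administration. The effect is confined to the safety description of the consequences of errors. The primary endpoint, receipt of the card and the medication-error proportion do not change.

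Three stronger readings are tempting, and the protocol does not support them:

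- A reader might infer that the study exists to monitor infection. Infection is not an endpoint; Section 7.1 names it as a consequence of the errors the study measures.
- A reader might infer that infection symptoms in general are excluded. Only some localising ones are.
- A reader might infer that one lost culture would be a large, calculable share of the evidence on consequences. That presupposes an event whose probability is nowhere stated, and it ignores the fever, consultation and replacement-dose data sought at every application.

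The conclusion assumes that Section 11.2 is applied as written and that relevant results occasionally reach the study.

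**What to change.** Add a sentence to Section 11.2: the exemption does not apply to infection-related Appendix G terms (the culture rows, bacterial and viral conjunctivitis, productive cough, increased sputum, dysuria) when the event is serious, or when a device issue, an incomplete, late or missed dose, or a replacement dose is reported for that administration. Deleting those rows from Appendix G would also work, but is broader than necessary.

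Align Section 9.7.3 with the rule by saying whether exempted events reported in the questionnaire are coded and tabulated. Any tabulation by medication-error status can be left to the SAP.

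The cost is a wording change in two sections and a small number of additional safety reports. These are bounded by about 80 respondents, at most about 280 applications, and a 72-hour window for each. The sample size and the analysis of the main estimates are not affected.
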